1.2 Primary Study Endpoints

Outcomes to be assessed

1. Extent of dermatomal sensory loss
2. Duration of sensory loss
3. Anatomical extent of injectate spread using MRI imaging. MRI data will not be collected after May 2023
4. Venous plasma concentration of ropivacaine at periodic time intervals

We are comparing these outcomes between

1. 20ml ropivacaine 0.5% with epinephrine vs no epinephrine

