2.0 Background

2.1 Scientific Background and Gaps

Thoracic surgery is associated with significant postoperative pain and providing adequate analgesia in these patients is essential for enhanced recovery protocols¹. Regional anesthesia

techniques, such as thoracic epidural and thoracic paravertebral blockade, are therefore commonly employed². These techniques have limitations however; they require a high degree of technical expertise, are contraindicated if the patient has a coagulopathy, and are associated with significant adverse effects and risk of complications. These include, but are not limited to hypotension, pneumothorax, and epidural abscess or hematoma formation. We recently described a novel ultrasound-guided regional anesthetic technique for providing thoracic analgesia, the ultrasound-guided Erector Spinae Plane (ESP) block. The ESP block involves injection of local anesthetic into the musculofascial plane deep (anterior) to the erector spinae muscle and superficial (posterior) to the tip of the transverse processes of the thoracic spine. Our radiological and anatomical investigation in fresh adult cadavers has shown that injection of a clinically-relevant volume (20ml) at the T5 vertebral level produces extensive spread of injectate within the erector spinae musculofascial plane, along the Para spinal and posterior chest wall, and extending between C4 and T12 vertebral levels³. This corresponds with early clinical experience indicating that the ESP block is effective in treating chronic thoracic pain³, acute post-thoracic surgical pain⁴⁻⁶, and pain from rib fractures⁷. It thus appears to provide similar analgesia to a thoracic paravertebral block, while being technically simpler and safer to perform. The ESP block therefore has promise as a simple, safe, yet highly effective method of providing thoracic analgesia, and one that can be learned and performed by the majority of anesthesiologists.

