2.2 Previous Data

Ultrasound-guided ESP injections of a clinically relevant volume (20 mL) of normal saline (with iodinated contrast and methylene blue) at the T5 vertebral level were performed in fresh cadavers. The cadavers underwent computed tomography imaging and anatomical dissection. The radiological and anatomical findings demonstrated a distribution of injectate within the erector spinae musculofascial plane, along the Para spinal and posterior chest wall, and extending between C4 and T12 vertebral levels [4]. It is unclear how the extent of spread may have been influenced by the state of preservation of the cadaver, post mortem tissue desiccation, temperature difference, and lack of perfusion and respiratory motion that would be present in a living subject. Even though the ESP block has not been studied extensively for evaluation of mechanism of action, there are a number of case reports and case series that have been published in the last year, where ESP has been shown to be safe in different conditions of use. [4-6] To date, there are 39 manuscripts that have been published and indexed in PubMed, and no associated complications or side effects have been reported. A list of those publications can be found using the following link:

<https://www.ncbi.nlm.nih.gov/pubmed/?term=erector+spinae+plane+block>. Here at the Penn State Hershey Medical Center, more than two hundred of these blocks have been performed for different procedures, without any complications or side effects.

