The subject will be placed in a sitting position, the skin over their upper back will be disinfected with chlorhexidine 2%, and the tip of the T5 transverse process on one side will be identified using a low-frequency curvilinear ultrasound transducer (Sonosite, Bethesda, USA) placed in a longitudinal parasagittal orientation as previously described. [4] The skin over the needle insertion site will be anesthetized with 2ml of lidocaine 1% conc. for patient comfort. A 22-gauge 10cm Tuohy needle (Stimuplex, BBraun, and Bethlehem, USA) will be inserted in-plane with the ultrasound beam to contact the T5 transverse process. One ml of 0.9% normal saline will be injected to confirm correct needle tip placement separating the ESP from transverse process, as evidenced by visible linear fluid spread deep to the erector spinae muscle. Injection of the specific volume and type of fluid according to the randomization group (see above) will then take place. MRI part of study stopped May 2023. After the completion of the assigned injection they will be transported to the MRI suite at the MRI core facility on the Hershey campus in a wheel chair. The subject will undergo two MRI's to determine the spread of the anesthetic. These will take place at approximately 30 and 90 minutes following the completion of the assigned block.

Following the Block injection (completion of the MRI data May 2023), the subjects will be allowed to sit, stand or lay down for the remainder of the study. Continuous monitoring and recording of vital signs will take place as, blood pressure and heart rate will be measured every 5 minutes, starting prior to performing the block, till 60 minutes after the block is performed and every 15 minutes thereafter for the duration of the study. A member of the research team blinded to the randomization allocation will perform a sensory assessment for loss of sensation to cold using ethanol on the skin at 20, 60, 120, 240, and 360 mins after the injection of active drug. The extent of sensory loss to cold will be marked on the body using a water-soluble color marker each time and will be photographed each time interval. A binary scoring system will be used for both assessments: 1 = reduced sensation; 2 = normal sensation.

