8.3 Statistical methods

Statistics: The statistical analysis will be performed using STATA 14.1 statistical software (StataCorp LP, College Station, TX) and Wilcoxon matched-pairs U test will be utilized for different MRI measurements and calculations. The χ^2 test will be used to analyze the differences between dermatomal anesthesia on hemi-thorax and abdomen.

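### The only named sensory test in Section 8.3 does not measure extent of sensory loss per subject or by arm, and no list of dermatomes says whether cervical levels are tested

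*Combined protocol and SAP*

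**What the plan says.** Section 1.2 puts "Extent of dermatomal sensory loss" first among the primary endpoints. It sets no anatomical limit and says the listed outcomes are compared between the groups with and without epinephrine. Section 1.1 makes defining that extent a primary objective.

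Section 7.2.1 describes the measurement. Sensation to cold is tested at 20, 60, 120, 240 and 360 minutes: "The extent of sensory loss to cold will be marked on the body using a water-soluble color marker each time". Each reading is photographed and a binary code (reduced or normal) is used. The section does not list the dermatomes or test points, or say where testing starts and stops.

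Section 8.3 has one sentence on sensory data: a chi-square test will be used for the "differences between dermatomal anesthesia on hemi-thorax and abdomen". Section 8.2 calls the study a pilot whose descriptive results will serve to plan a larger trial, without saying what those results are.

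Sections 2.1 and 2.2 describe the sponsor's cadaver work with 20 ml at T5, which showed spread "extending between C4 and T12 vertebral levels".

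**The concern.** The endpoint asks how far the block reaches. The named test does not answer that. A chi-square on presence or absence of anesthesia by body region gives no highest level, no lowest level and no count for a subject, and the sentence does not mention the two arms.

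The regions named are also narrower than the range the protocol itself reports. The chi-square sentence mentions no cervical level, although the cadaver range begins at C4. If epinephrine changed upward spread, the named test would not be the place to see it.

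The missing list of levels adds a second difficulty. If the neck or arm is unmarked in a photograph, nobody can say later whether it was tested and found normal. An upper limit that arises because testing stopped would look like a true upper limit. This matters more since MRI ended in May 2023: for subjects studied after that, the cold map is the only direct measure of where the block reached.

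**Working it through.** The documents give no figure for this point that could be reproduced. The sample size of 12 (6 per group) has no calculation behind it and is not in dispute. The check compares scope and counts levels.

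**Step 1. Endpoint, measurement and analysis side by side**

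| Item | Section | Regional limit | Per-subject measure of extent | Comparison of arms |
|---|---|---|---|---|
| Endpoint | 1.2 | none | named, not defined | yes |
| Measurement | 7.2.1 | none stated; no list of levels | outline and photograph, binary code | not applicable |
| Named test | 8.3 | hemi-thorax and abdomen | none | not mentioned |

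The test matches the endpoint in none of the three columns.

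**Step 2. Two readings of the Section 8.3 sentence**

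- It may define the field analysed, thorax plus abdomen. Cervical levels then fall outside the test.
- It may compare anesthesia on the thorax with anesthesia on the abdomen. It then does not define a field.

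On either reading the result is neither an extent per subject nor a contrast between epinephrine and no epinephrine. This part of the point therefore does not depend on which reading is right.

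**Step 3. Size of the gap on the first reading**

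Inputs: the range C4 to T12 (Sections 2.1 and 2.2), and the assumption that hemi-thorax and abdomen means T1 to T12. The documents list no dermatomes, so the second input is a reading and not a fact.

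- Vertebral levels in the range: C4 to C7 = 4; T1 to T12 = 12; total 4 + 12 = 16.
- Share above T1: 4 / 16 = 25%.
- Counted as dermatomes, where C8 exists: C4 to C8 = 5; total 5 + 12 = 17; share 5 / 17 = 29%.

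These are shares of a cadaver range of injectate. They are not shares of sensory data lost.

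**Step 4. Can Section 7.2.1 recover the cervical information?**

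Partly. Loss above T1 that the assessor finds can be outlined and photographed. Absence of an outline is ambiguous, because nothing records which levels were tested. Section 8.2 does not promise that the highest or lowest level will be reported.

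**The case against.** A reader might infer that cervical loss is not counted, that the endpoint is cut off at the top of the chest, or that a difference in upward spread cannot appear. The documents do not support any of these. The endpoint has no regional limit, Section 7.2.1 marks and photographs loss with no anatomical boundary, and Section 8.2 plans descriptive results that are not confined to the trunk. Only the named test leaves the cervical levels out.

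A reader might also infer that numbness of the neck, shoulder or arm is expected, or that a true extent of 17 dermatomes would be reported as 12. Neither follows. The injections were "at the T5 vertebral level were performed in fresh cadavers", and the finding was a "distribution of injectate within the erector spinae musculofascial plane, along the Para spinal and posterior chest wall". That is not sensory loss. Section 2.2 adds its own caution: "It is unclear how the extent of spread may have been influenced by the state of preservation of the cadaver". The range is given without the number of cadavers or how often each level was reached, so it does not show that C4 is typical. The contrast of 17 with 12 needs skin loss to match cadaver spread and also needs the T1 to T12 reading.

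These objections stand, and they limit the point to the named test and to the missing list of levels. They do not answer the mismatch in Step 1, or the ambiguity of an unmarked area. Section 2.3 says that the extent of sensory blockade in living subjects is not yet known, which is a reason to record where testing stopped.

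A further fair objection is that adding levels during the study may make earlier and later subjects less comparable, in a study of only 12. That is a real cost, and it is the reason for an explicit rule on untested levels.

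**Conclusion.** The point holds as an underspecified analysis of the first primary endpoint. Section 8.3 names a test that does not yield extent of sensory loss per subject, does not name the comparison of arms that Section 1.2 requires, and mentions no cervical level. Section 7.2.1 lists no levels, so an area tested and normal cannot be separated from one that was not tested.

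On the assumption that the Section 8.3 region is T1 to T12, the part of the cadaver range outside the test is 25% of vertebral levels, or 29% if counted as dermatomes. How much sensory loss lies there is unknown. It could be none. The case for change rests mainly on the mismatch of test and endpoint, which needs no assumption; the cervical range is a supporting reason for where the list of levels should start. It is an inexpensive improvement that the sponsor should make.

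**What to change.** **Section 7.2.1.** List the dermatomes to be tested at each of the five readings, covering the cervical levels from C4 downward and all levels to T12. Score each one as reduced, normal or not tested. With 17 dermatomes and five readings this is 17 × 5 = 85 scores per subject.

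**Section 8.3.** Replace the chi-square by three measures per subject at each reading: highest blocked level, lowest blocked level and number of blocked dermatomes. Summarise them by arm and compare the groups with and without epinephrine. With 6 per group, every subject's values can be listed.

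Add two rules. Where loss reaches the last level tested, report the limit as at or beyond that level. Treat untested levels as missing, not normal, so that a count from an incomplete reading is shown as a minimum.

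**Subjects already studied.** Use the stored photographs to see what was marked, and leave unmarked cervical areas as missing unless a record shows that they were tested.

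**Cost.** Changes to the wording of two sections and a few more minutes per reading. The sample size stays at 12. Subjects already studied may lack cervical readings except as seen on the photographs, so summaries of the highest level may rest on fewer than 12 subjects or contain values known only as at or beyond a level.

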9.0 Confidentiality, Privacy and Data Management

See the Research Data Plan Review Form.

10.0 Data and Safety Monitoring Plan

10.1 Periodic evaluation of data

The PI and research coordinator will review cumulative adverse events, early termination of study participation, and accrual every six months and report any issues requiring modification of the study or alteration of the risk: benefit ratio to the IRB immediately. A summary of adverse events, study progress and protocol modifications will be included for IRB review in the continuing review.

10.2 Data that are reviewed

The data to be reviewed will be:

- Safety data
- Untoward events
- Efficacy data

10.3 Method of collection of safety information

Safety information will be collected by the research coordinator at study visits and follow-up phone call.

10.4 Frequency of data collection

See table below

Frequency of data collection, including when safety data collection starts								
		Conse nt	Placeme nt of IV	Collecti on of blood samples	MRI Remov e May 2023	Monitori ng of Vitals	Phon e calls	Senso ry Evals
	Pre Procedure Visit	X		X				
The day of Procedure	On Arrival		X	X		X		
	5mts					X		
	10					X		
	15					X		
	20			X		X		X
	25					X		
	30				X	X		
	35					X		
	40			X		X		
	45					X		
	50					X		
	55					X		
	60			X		X		X
	75					X		
	90			X	X	X		
	105					X		
	120			X		X		X
	135					X		
	150					X		
	165					X		
	180					X		
	195					X		
	210					X		
	225					X		

	240			X		X		X
	255					X		
	270					X		
	285					X		
	300					X		
	315					X		
	330					X		
	345					X		
	360					X		X
	Post Procedure Day 1						X	
	Post Procedure Day 2						X	

10.5 Individuals reviewing the data

Oversight for the conduct of the study will be provided by the PI and the research coordinator will monitor the data. They will ensure that all eligible criteria and consent requirements are met prior to a subjects' participation in the study and that the procedures and adverse event reporting occur according to the IRB approved protocol.

10.6 Frequency of review of cumulative data

The PI and research coordinator will review cumulative adverse events, early termination of study participation, and accrual every six months and report any issues requiring modification of the study or alteration of the risk: benefit ratio to the IRB immediately. A summary of adverse events, study progress and protocol modifications will be included for IRB review in the continuing review.

10.7 Statistical tests

Not applicable

10.8 Suspension of research

The study will be immediately suspended if there is any report or occurrence of serious side effect to any of the subjects. The serious side effects include but not limited to Infection, sepsis, severe hypotension, severe hypertension, any condition requiring to air way management,

11.0 Risks

The risks to you include:

Venipuncture: The discomfort associated with removing blood by venipuncture (by needle from a vein) is a slight pinch or pin prick when the sterile needle enters the skin. The risks include mild discomfort and/or a black and blue mark at the site of puncture. Less common risks include a small blood clot, infection or bleeding at the puncture site, and on rare occasions fainting during the procedure.

Regional Anesthesia - Possible complications and discomforts from regional anesthesia include:

- Common – local/pain and/or discomfort, infection, and/ or headache
- Uncommon – shock or extreme fall in blood pressure, convulsions and/or seizures
- Rare – nerve damage resulting in numbness, tingling and/or paralysis which may be temporary or permanent. Respiratory arrest, cardiac arrest, and/or allergic reaction to drugs. Death.

Ropivacaine Hydrochloride: Possible complications and discomforts from ropivacaine hydrochloride include:

- Incidence 5% or greater – High blood pressure, nausea, vomiting, fever, headache, back pain, low blood pressure, and slow heartbeat.
- Incidence 1% to 5% - Urinary retention, dizziness, shaking or exaggerated shivering, rapid heart rate, anxiety, production of abnormally small amounts of urine, reduced sense of touch or sensation, chest pain, deficiency of potassium in the bloodstream.

Epinephrine:

- Side effects of epinephrine include: Fast heartbeat, sweating, headache, weakness, shakiness, paleness, and dizziness.

Procedural risks:

- It will involve the similar procedural risk as other peripheral regional anesthesia procedures. This procedure has not been studied very extensively so the literature of its safety is not known completely. However, there are a number of case reports and case series that have been published in the last year, where ESP has been shown to be safe in different conditions of use.[4-6] Here at the Penn State Hershey Medical Center, more than two hundred of these blocks have been performed for different procedures, without any complications or side effects.
- There is a rare risk of pneumothorax, which is getting air or gas in the cavity between the lungs and the chest wall, causing collapse of the lung.
- Venipuncture: Any time we insert a needle in your body there is a minimal risk for bruise, infection or extravasation of blood.

MRI removed May 2023

MRI discomfort and risks -- Because the MRI scanner contains a very strong magnet, you may not be able to have the MRI if you have certain kinds of metal in your body (for example, a heart pacemaker, a metal plate, certain types of heart valves or brain aneurysm clips). Someone will ask you questions about this before you have the MRI. Having a MRI may mean some added discomfort to you. In particular, you may be uncomfortable inside the MRI scanner if you do not like to be in closed spaces (“claustrophobia”). You may also be bothered by the loud banging noise during the study. Temporary hearing loss has been reported from the loud noise. This is why you will be asked to wear earplugs. During the procedure, you will be able to talk with the MRI staff through a speaker system. You can tell them to stop the scan at any time.

You should not expect to get your results from the MRI scan since the scan done during this study is not designed to detect or evaluate any medical condition you may have. The MRI scan is intended solely for research purposes and will not provide the same detailed information as an MRI done for clinical reasons. There is a small chance that researchers could find something that might be important to your health. If this happens, a member of the study team may contact you to find out if you would like to learn more. However, even if we find something important to your health, we cannot guarantee that you will be contacted.

Risk of loss of confidentiality: There is a risk of loss of confidentiality if your information or your identity is obtained by someone other than the investigators, but precautions will be taken to prevent this from happening. The confidentiality of your electronic data, created by you or by the researchers, will be maintained to the degree permitted by the technology used. Absolute confidentiality cannot be guaranteed.

12.0 Potential Benefits to Subjects and Others

12.1 Potential Benefits to Subjects

You will not experience any direct benefit from this research.

12.2 Potential Benefits to Others

Presently there is no outcome and other related data available for this procedure. The results of this research may guide the future use of ESP Blocks by providing providers with a better understanding of the technique and its associated effect and may help improve the practice of ESP blocks for patients in the future.

13.0 Sharing Results with Subjects

Results will not be shared with the participants.

14.0 Subject Stipend (Compensation) and/or Travel Reimbursements

Participants will receive \$300 for the time they have given for participation in this research study. If they do not complete the study for any reason, they will be paid for the visits they have completed:

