1.3 Secondary Study Endpoints

1. Hemodynamic parameters at periodic time intervals
2. Any adverse effects or side effects related to injection of the medications

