3.3 Early Withdrawal of Subjects

3.3.1 Criteria for removal from study

- Subject does not complete the study
- Develop any complications or side effects due to injections.
- Abnormal Creatinine level following baseline blood test
- Subject does not follow fasting rules

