3.3.2 Follow-up for withdrawn subjects

Any subject withdrawn from the study due to complications or side effects of the injection will be seen immediately by the PI and a course of treatment will be determined.

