7.1.1 Randomization process

The subjects enrolled will be randomized into two groups (6 participants in each group) by a computer-generated randomization list using SAS software (SAS Institute, Cary, NC):

Randomization groups

1. Group RE will have 20mL of **0.5% Ropivacaine with epinephrine** injected at the left or right T5 transverse process.
2. Group R will have 20mL of **0.5% Ropivacaine without epinephrine** injected at the left or right T5 transverse process.

The randomization will be performed, using a sealed envelope technique, and will be stratified according to the side of the injections (either left or right) so that each arm will have equal number of left and right sided ESP blocks. This will be done by the investigational pharmacy while preparing the medications. All subjects, the anesthesiologist performing the procedure, the radiologist, and the research coordinator collecting the data will be blinded and will not be aware of the details of the injection and allocation of the participants. In the event that the patient has a concerning reaction or becomes unstable in any fashion, the patient will be immediately unblinded and removed from the study.

The conduct of the study will be as follows.

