15.0 Economic Burden to Subjects

15.1 Costs

There is no cost to participants for taking part in this study.

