15.2 Compensation for research-related injury

It is the policy of the institution to provide neither financial compensation nor free medical treatment for research-related injury. In the event of injury resulting from this research, medical treatment is available but will be provided at the usual charge. Costs for the treatment of research-related injuries will be charged to subjects or their insurance carriers.

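### Sections 3.3.1 and 14.0 together allow a volunteer removed for a side effect to be paid less, which may discourage symptom reporting on a secondary endpoint (minor)

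*Combined protocol and SAP*

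**What the plan says.** - **Payment.** Section 14.0 pays each participant $300 "for the time they have given for participation in this research study". For non-completers it continues: "If they do not complete the study for any reason, they will be paid for the visits they have completed". No split of the $300 by visit appears in the text available for review. It may have been lost in extraction or lie in the removed consent pages, so its absence is not counted as a fault.
- **Removal.** Section 3.3.1 lists as a criterion "Develop any complications or side effects due to injections", with no severity threshold. Section 7.1.1, repeated in 7.4.5, adds that after a concerning reaction or instability "the patient will be immediately unblinded and removed from the study".
- **After removal.** Under section 3.3.2 a subject withdrawn for such a reason "will be seen immediately by the PI and a course of treatment will be determined". It does not mention payment.
- **Endpoint.** The second item in section 1.3 is "Any adverse effects or side effects related to injection of the medications". Section 10.3 has the research coordinator collect safety information at visits and by phone.
- **Costs.** Section 15.1 states: "There is no cost to participants for taking part in this study". Section 15.2 states, as institutional policy: "Costs for the treatment of research-related injuries will be charged to subjects or their insurance carriers".

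**The concern.** The volunteers who supply the symptom data are the same people whose payment may fall if they supply it. They are healthy, paid, and have no direct benefit from taking part (section 12.1). Nausea, headache, back pain and dizziness do not show on an ECG, a blood-pressure cuff or an oximeter. They reach the record mainly when the volunteer mentions them.

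If a volunteer did keep quiet, the error would run one way, toward fewer recorded events. Section 8.2 says the descriptive results will be used to plan a larger randomised trial, and section 11.0 concedes that the safety literature on this block is incomplete. An understated side-effect rate would therefore be carried into later planning.

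**Working it through.** The plan gives no figure on this point to reproduce. The check is mainly a reading of the sections side by side, followed by an illustration of scale.

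**1. Does the text link a reported symptom to lower pay?**
- A symptom attributed to the injection meets a removal criterion at any severity (3.3.1).
- A removed subject has not completed the study.
- Non-completion for whatever reason is paid by completed visit (14.0).
- No safety exemption appears in 3.3.1, 3.3.2, 7.1.1, 7.4.5 or 14.0.

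The link therefore exists on the procedure day. It needs 3.3.1 and 14.0 read together; neither section shows it alone.

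**2. How much money?** Let *a* be the amount attached to visits completed by the time of removal. The loss is 300 − *a*. Since *a* is not shown, the loss lies somewhere from $0 to $300. The $300 end would require that the pre-procedure visit carries no payment and that a part-completed procedure day counts as not completed. The documents settle neither point.

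**3. Which data are exposed?** Blood pressure and heart rate follow a fixed schedule: every 5 minutes to 60 minutes, then every 15 minutes (7.2, 7.4.4). Vomiting during the 360 + 30 = 390 minutes on site would be visible to staff. What remains is self-reported symptoms.

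**4. How many subjects might have such a symptom?** Section 11.0 puts nausea, headache and back pain each at 5% or more. Take exactly 5% each as an assumption; it is the floor of the stated range. The share of subjects with at least one of the three is then:
- complete overlap: 5%, or 12 × 0.05 = 0.6 subjects;
- independence: 1 − 0.95³ = 14.3%, or 1.7 subjects;
- no overlap: 3 × 5% = 15%, or 1.8 subjects.

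Adding vomiting as a fourth gives 1 − 0.95⁴ = 18.5% under independence and 20% without overlap. These are expected subjects with symptoms, not suppressed reports.

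**5. What would incomplete reporting do at n = 12?** Let *p* be the true incidence and *r* the share reported. The chance of recording at least one event is 1 − (1 − *pr*)¹². No value of *r* can be derived from the documents; all values below 1 are assumptions, and *p* = 10% is also assumed.

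| *r* | *p* = 5% | *p* = 10% |
|---|---|---|
| 1 | 46.0% | 71.8% |
| 0.9 | 42.5% | 67.8% |
| 0.75 | 36.8% | 60.8% |
| 0.5 | 26.2% | 46.0% |

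For example, at *p* = 5% and *r* = 0.5: 1 − 0.975¹² = 26.2%. Expected recorded events fall from 12 × 0.05 = 0.60 to 0.30.

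**The case against.** The strongest reply is that nothing in the documents shows that anyone is discouraged from reporting. That stands, and the point can only be worded as something that may happen. The plan also has safeguards: the coordinator asks about safety, two follow-up calls use a script, and subjects go home with a note asking them to report anything unusual (7.2, 7.3, 10.3). These reduce the risk of under-reporting but do not remove the payment link.

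Several stronger readings are tempting, and the documents do not support them.
- *A symptom mentioned at a follow-up call also costs money.* By then both in-person visits are done. Section 10.3 names study visits and the phone call separately, and nothing says a call is a paid visit.
- *Reporting a symptom leads to a bill.* Section 15.2 covers treatment of a research-related injury, and an insurer may bear it. Mentioning nausea incurs no charge under that text.
- *Hidden symptoms would defeat the suspension rule.* Section 10.8 requires a serious side effect. Its examples do not include these mild symptoms, and severe blood-pressure change would show on scheduled monitoring.
- *The comparison of the two groups is biased.* The rule is the same for both, so only the overall rate is in question.

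It can also be said that 12 subjects give little safety information anyway. With no event in 12, the one-sided 95% upper bound is 1 − 0.05^(1/12) = 22.1% even with full reporting. That is fair and limits the priority, but it is no reason to keep an avoidable disincentive.

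**Conclusion.** The point holds in a limited form. Sections 3.3.1 and 14.0 together allow a volunteer who reports a side effect on the procedure day to be removed and paid only for completed visits, with no exemption for safety removals. This may discourage disclosure of self-reported symptoms and may bias the overall rate of the secondary side-effect endpoint downward.

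A reader might infer that the plan does discourage reporting and does bias the endpoint. The documents do not establish that: whether under-reporting occurs, its size, and the sum at stake cannot be derived from them. The figures above rest on an incidence at the floor of section 11.0 (or an assumed 10%) and on assumed reporting shares, and serve only to show that one or two unreported events could matter among 12 subjects. Priority: minor.

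**What to change.** Add to section 14.0 and the consent form, in words such as: *A subject who has received the injection and whose participation ends because of a side effect, a complication or a safety decision is paid as if the study had been completed. Reporting symptoms never reduces payment.* Keep payment by completed visit for voluntary non-completion and for subjects who do not go on to the block.

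No removal, treatment or other clinical rule changes. Section 15.2 is institutional policy and is context here, not part of the change.

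The cost is at most the unpaid remainder of $300 for each injected subject removed for safety. A total cannot be given, because the number of such removals is unknown. Nor is 12 × $300 = $3,600 a firm ceiling on payments to injected subjects: section 8.1 asks for 12 completers, so replacing someone removed after the block would take the number injected above 12.
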